### Specifications by Methods of Measurements

The same method of assessment and the same technique should be used to characterise each identified and reported lesions at baseline, during treatment and at the post-treatment assessment. Image-based evaluation is preferred to evaluation by clinical examination when both methods have been used to assess the anti-tumour effect of a treatment. CT is the best currently available and reproducible method for measuring target lesions selected for response assessment. Investigators should utilize the best available CT imaging technique available to them for determining response and PFS of patients participating in the PePS2 trial.

## Tumour Response Evaluation

### Baseline Documentation of "Target" and "Non-target" Lesions

All measurable lesions up to a maximum of 2 lesions per organ and 5 lesions in total, representative of all involved organs, should be identified as "target" lesions and recorded and measured at baseline.

Target lesions should be selected on the basis of their size (those with the longest diameter) and their suitability for accurate, reproducible, repeated measurements.

A sum of the longest diameter (LD) for all target lesions will be calculated and reported as the baseline sum LD. The baseline sum LD will be used as the reference by which to characterise the objective tumour response.

All other lesions (or sites of disease) should be identified as "non-target" lesions and should also be recorded at baseline. Measurements of these lesions are not required but these lesions should be followed as 'present', 'absent' or in rare cases 'unequivocal progression' and recorded.

### Response Criteria

#### A. Evaluation of Target Lesions

Response Category	Description
Complete Response (CR)	Disappearance of all target lesions
Partial Response (PR)	At least a 30% decrease in the sum of the LD of target lesions, taking as reference the baseline sum LD
Progressive Disease (PD)	At least a 20% increase in the sum of the LD of target lesions, taking as reference the smallest sum LD recorded since the treatment started or the appearance of one or more new lesions. In addition to this, the sum must also demonstrate an absolute increase of at least 5 mm. The appearance of one or more lesion is also considered progression.
Stable Disease (SD)	Neither sufficient shrinkage to qualify for PR nor sufficient increase to qualify for PD, taking as reference the smallest sum LD since the treatment started

#### B. Evaluation of Non-target Lesions

Response Category	Description
Complete Response (CR)	Disappearance of all non-target lesions
Incomplete Response/ Stable Disease (SD)	Persistence of one or more non-target lesion(s)
Progressive Disease (PD)	Appearance of one or more new lesions and/or unequivocal progression of existing non-target lesions 

#### Notes:

1. To achieve "unequivocal progression" on the basis of the non-target disease, there must be an overall level of substantial worsening in non-target disease such that, even in presence of SD or PR in target disease, the overall tumour burden has increased sufficiently to merit discontinuation of therapy.

### **C. Evaluation of Best Overall Response**

The best overall response is the best response recorded from the start of treatment until disease progression. In general, the patient's best response assignment will depend on the achievement of both measurement and confirmation criteria.

### **D. Overall Responses for all Possible Combinations of Tumour Responses in Target and Non-target Lesions With or Without the Appearance of New Lesions**

Target Lesions	Non-target Lesions	New Lesions	Overall Response
Complete response (CR)	CR	No	CR
Complete response (CR)	Non-CR/non-PD	No	PR
Complete response (CR)	Not evaluated	No	PR
Partial response (PR)	Non-PD	No	PR
Stable disease (SD)	Non-PD	No	SD
Not all evaluated	Non-PD	No	Not evaluable (NE)
Progressive disease (PD)	Any	Yes or no	PD
Any	PD	Yes or no	PD
Any	Any	Yes	PD

Patients with a global deterioration of health status requiring discontinuation of treatment without objective evidence of disease progression at that time should be classified as having "symptomatic deterioration." Every effort should be made to document the objective disease progression, even after discontinuation of treatment.

#### **Frequency of Tumour Re-evaluations**

For the PePS2 trial, clinical response rate, durable clinical benefit (CR+PR+SD $\geq$ 18 weeks), PFS and duration of response will be evaluated radiologically by a CT scan of the chest and abdomen and other clinically relevant areas at baseline and at 9 weekly intervals and by clinical measurement at 3 weekly intervals until progression or discontinuation of trial medication. The final CT scan should be performed within 28 days of discontinuation of trial medication.

For patients who discontinue treatment prior to progression CT scans and clinical measurements should, where possible, continue to be performed in accordance with the relevant schedule of assessments.

### Appendix 3: Cockcroft and Gault equation

Cockcroft and Gault creatinine clearance (CrCl):

$$\text{CrCl (mL/min)} = \frac{N \times [140 - \text{age (years)}] \times \text{weight (kg)}}{\text{Serum creatinine (micromol/L)}}$$

Where N = 1.23 males, 1.04 females

#### Appendix 4: Charlson Index

The Charlson Index (30) will be used in this trial for the assessment of comorbidity.

Score	Condition
1	Myocardial infarction (history, not ECG changes only) Congestive heart failure Peripheral vascular disease (includes aortic aneurysm $\geq 6$ cm) Cerebrovascular disease: CVA with mild or no residua or TIA Dementia Chronic pulmonary disease Connective tissue disease Peptic ulcer disease Mild liver disease (without portal hypertension, includes chronic hepatitis) Diabetes without end-organ damage (excludes diet-controlled alone)
2	Hemiplegia Moderate or severe renal disease Diabetes with end-organ damage (retinopathy, neuropathy, nephropathy, or brittle diabetes) Tumour without metastasis (exclude if $>5$ years from diagnosis) Leukemia (acute or chronic) Lymphoma
3	Moderate or severe liver disease
6	Metastatic solid tumour AIDS (not just HIV positive)
NOTE: For each decade $>40$ years of age, a score of 1 is added to the total score.	
Abbreviations: ECG, electrocardiogram; CVA, cerebrovascular accident; TIA, transient ischemic attack; AIDS, acquired immunodeficiency syndrome; HIV, human immunodeficiency virus	

## Appendix 5: Quality of Life Questionnaires

### A. Functional Assessment of Cancer Therapy – Lung (FACT-L)

\*as available on [www.facit.org](http://www.facit.org)

Below is a list of statements that other people with your illness have said are important. Please circle or mark one number per line to indicate your response as it applies to the past 7 days.

PHYSICAL WELL-BEING		Not at all	A little bit	Some -what	Quite a bit	Very much
-----------------------------------	--	-------------------	---------------------	-------------------	--------------------	------------------

GP1	I have a lack of energy .....	0	1	2	3	4
GP2	I have nausea.....	0	1	2	3	4
GP3	Because of my physical condition, I have trouble meeting the needs of my family .....	0	1	2	3	4
GP4	I have pain.....	0	1	2	3	4
GP5	I am bothered by side effects of treatment.....	0	1	2	3	4
GP6	I feel ill.....	0	1	2	3	4
GP7	I am forced to spend time in bed.....	0	1	2	3	4

SOCIAL/FAMILY WELL-BEING		Not at all	A little bit	Some -what	Quite a bit	Very much
--	--	-------------------	---------------------	-------------------	--------------------	------------------

GS1	I feel close to my friends.....	0	1	2	3	4
GS2	I get emotional support from my family .....	0	1	2	3	4
GS3	I get support from my friends .....	0	1	2	3	4
GS4	My family has accepted my illness.....	0	1	2	3	4
GS5	I am satisfied with family communication about my illness.....	0	1	2	3	4
GS6	I feel close to my partner (or the person who is my main support) .....	0	1	2	3	4

*Regardless of your current level of sexual activity, please answer the following question. If you prefer not to answer it, please mark this box  and go to the next section.*

GS7	I am satisfied with my sex life .....	0	1	2	3	4
-----	---------------------------------------	---	---	---	---	---

Please circle or mark one number per line to indicate your response as it applies to the past 7 days.

EMOTIONAL WELL-BEING		Not at all	A little bit	Some -what	Quite a bit	Very much
-----------------------------	--	------------	--------------	------------	-------------	-----------

GE1	I feel sad.....	0	1	2	3	4
GE2	I am satisfied with how I am coping with my illness .....	0	1	2	3	4
GE3	I am losing hope in the fight against my illness ..	0	1	2	3	4
GE4	I feel nervous.....	0	1	2	3	4
GE5	I worry about dying .....	0	1	2	3	4
GE6	I worry that my condition will get worse .....	0	1	2	3	4

FUNCTIONAL WELL-BEING		Not at all	A little bit	Some -what	Quite a bit	Very much
------------------------------	--	------------	--------------	------------	-------------	-----------

GF1	I am able to work (include work at home) .....	0	1	2	3	4
GF2	My work (include work at home) is fulfilling.....	0	1	2	3	4
GF3	I am able to enjoy life.....	0	1	2	3	4
GF4	I have accepted my illness .....	0	1	2	3	4
GF5	I am sleeping well.....	0	1	2	3	4
GF6	I am enjoying the things I usually do for fun.....	0	1	2	3	4
GF7	I am content with the quality of my life right now .....	0	1	2	3	4

ADDITIONAL CONCERNS		Not at all	A little bit	Some -what	Quite a bit	Very much
----------------------------	--	------------	--------------	------------	-------------	-----------

B1	I have been short of breath.....	0	1	2	3	4
C2	I am losing weight.....	0	1	2	3	4
L1	My thinking is clear.....	0	1	2	3	4
L2	I have been coughing .....	0	1	2	3	4
B5	I am bothered by hair loss .....	0	1	2	3	4
C6	I have a good appetite.....	0	1	2	3	4
L3	I feel tightness in my chest .....	0	1	2	3	4
L4	Breathing is easy for me.....	0	1	2	3	4
Q3	Have you ever smoked? No ___ Yes ___ If yes:					
L5	I regret my smoking.....	0	1	2	3	4

**B. EQ-5D Questionnaire**

As available of [www.euroqol.org](http://www.euroqol.org) (31)

**C. Patient Generated Subjective Global assessment – Box 4**

**Box 4. Activities and Function:** Over the past month I would generally rate my activity as:

- 0- Normal with no limitations
- 1- Not my normal self, but able to be up and about with fairly normal activities
- 2- Not feeling up to most things, but in bed or chair less than half the day
- 3- Able to do little activity and spend most of the day in bed or chair
- 4- Pretty much bedridden, rarely out of bed

## Appendix 6: Common Terminology Criteria for Adverse Events (CTCAE), version 4.0

Toxicities will be recorded according to the Common Terminology Criteria for Adverse Events (CTCAE), version 4.0. The full CTCAE document is available on the National Cancer Institute (NCI) website, the following address was correct when this version of the protocol was approved: [http://ctep.cancer.gov/protocolDevelopment/electronic\\_applications/ctc.htm](http://ctep.cancer.gov/protocolDevelopment/electronic_applications/ctc.htm)

## Appendix 7: Adverse Event definition

### Adverse Event

Any untoward medical occurrence in a patient or clinical trial subject administered a medicinal product and which does not necessarily have a causal relationship with this treatment.

Comment:

An AE can therefore be any unfavourable and unintended sign (including abnormal laboratory findings), symptom or disease temporally associated with the use of an investigational medicinal product, whether or not related to the investigational medicinal product.

### Adverse Reaction

All untoward and unintended responses to an IMP related to any dose administered.

Comment:

An AE judged by either the reporting Investigator or Sponsor as having causal relationship to the IMP qualifies as an AR. The expression reasonable causal relationship means to convey in general that there is evidence or argument to suggest a causal relationship.

### Serious Adverse Event

Any untoward medical occurrence or effect that at any dose:

- Results in death
- Is life-threatening\*
- Requires hospitalisation\*\* or prolongation of existing inpatients' hospitalisation
- Results in persistent or significant disability or incapacity
- Is a congenital anomaly/birth defect
- Or is otherwise considered medically significant by the Investigator\*\*\*

Comments:

The term severe is often used to describe the intensity (severity) of a specific event. This is not the same as serious, which is based on patients/event outcome or action criteria.

\* Life threatening in the definition of an SAE refers to an event in which the patient was at risk of death at the time of the event; it does not refer to an event that hypothetically might have caused death if it were more severe.

\*\*Hospitalisation is defined as an unplanned, formal inpatient admission, even if the hospitalisation is a precautionary measure for continued observation. Thus hospitalisation for protocol treatment (e.g. line insertion), elective procedures (unless brought forward because of worsening symptoms) or for social reasons (e.g. respite care) are not regarded as an SAE.

\*\*\* Medical judgment should be exercised in deciding whether an AE is serious in other situations. Important AEs that are not immediately life threatening or do not result in death or hospitalisation but may jeopardise the subject or may require intervention to prevent one of the other outcomes listed in the definition above, should be considered serious.

### Serious Adverse Reaction

An Adverse Reaction which also meets the definition of a SAE.

### Suspected Unexpected Serious Adverse Reaction

A SAR that is unexpected i.e. the nature, or severity of the event is not consistent with the applicable product information.

A SUSAR should meet the definition of an AR, UAR and SAR.

## Unexpected Adverse Reaction

An AR, the nature or severity of which is not consistent with the applicable product information (e.g. Investigator Brochure (IB) for an unapproved IMP or (compendium of) Summary of Product Characteristics (SPC) for a licensed product).

When the outcome of an AR is not consistent with the applicable product information the AR should be considered unexpected.

## Events of Clinical Interest

Subjects should be assessed for possible ECIs prior to each dose. Lab results should be evaluated and subjects should be asked for signs and symptoms suggestive of an immune related event. Subjects who develop an ECI thought to be immune-related should have additional testing to rule out other etiologic causes. If lab results or symptoms indicated a possible immune-related ECI then additional testing should be performed to rule out other etiologic causes. If no other cause was found, then it is assumed to be immune-related (ir).

An irAE is defined as a clinically significant AE of any organ that is associated with study drug exposure, is of unknown etiology, and is consistent with an immune -related mechanism. It is possible that irAEs other than those listed may be observed in subjects receiving pembrolizumab; therefore, all AEs of unknown etiology associated with drug exposure should be evaluated to determine if it is possibly immune related. This is meant to be a general guidance; therefore, recommendations in the current document might not be all inclusive. As such Investigators are encouraged to contact the PePS2 Trial Office as needed to discuss cases that warrant separate discussion outside of the scope of current guidelines. Permanent discontinuation of pembrolizumab due to irAE may be subject of discussion between the Trial Office and treating Investigator.

The most commonly reported immune-related adverse events across the dose schedules are hypothyroidism (7.2%), pneumonitis (2.9%), hyperthyroidism (2.2%), colitis (1.3%) and skin AEOSI (1.3% including all terms). Based on the mechanism of action of pembrolizumab and similar immunomodulatory agents, MSD is interested in potential irAEs, and encourages appropriate investigation of signs and symptoms suggestive of these. Consultation with the appropriate medical specialist should be considered when investigating a possible irAE. These events can occur after the first dose to several months after the last dose of treatment. Mild irAEs are usually treated symptomatically and do not require dosing delays or discontinuation. Higher grade and persistent lower grade irAEs typically necessitate withholding or discontinuing treatment and administration of systemic steroids or other immunosuppressive agents (such as tumor necrosis factor blockers), when systemic steroids are not effective. Early recognition of irAEs and initiation of treatment are critical to reduce the risk of complications, since the majority of irAEs are reversible with the use of steroids and other immune suppressants

Most immune-related adverse reactions occurring during treatment with pembrolizumab were reversible and managed with interruptions of pembrolizumab, administration of corticosteroids and/or supportive care. Immune-related adverse reactions have also occurred after the last dose of pembrolizumab.

For suspected immune-related adverse reactions, adequate evaluation to confirm aetiology or exclude other causes should be ensured. Based on the severity of the adverse reaction, pembrolizumab should be withheld and corticosteroids administered. Upon improvement to Grade  $\leq 1$ , corticosteroid taper should be initiated and continued over at least 1 month. Based on limited data from clinical studies in patients whose immune-related adverse reactions could not be controlled with corticosteroid use, administration of other systemic immunosuppressants can be considered.

Pembrolizumab may be restarted within 12 weeks after last dose if the adverse reaction remains at Grade  $\leq 1$  and corticosteroid dose has been reduced to  $\leq 10$  mg prednisone or equivalent per day.

Pembrolizumab must be permanently discontinued for any Grade 3 immune-related adverse reaction that recurs and for any Grade 4 immune-related adverse reaction toxicity, except for endocrinopathies that are controlled with replacement hormones.

If an irAE does not resolve or improve to  $\leq$  Grade 1 within 12 weeks after last administration of pembrolizumab, study therapy discontinuation should be considered after discussion with PePS2 Trial Office.

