**Table 4: Dose modification and toxicity management guidelines for immune-related AEs associated with pembrolizumab**

Immune-related AEs	Toxicity grade or conditions (CTCAEv4.0)	Action taken to pembrolizumab	AE management with corticosteroid  and/or other therapies	Monitoring and Supportive Care
Pneumonitis	Grade 2	Withhold 	
 
Administer corticosteroids (initial dose of 1-2mg/kg prednisone or equivalent) followed by taper
 
	
 
Monitor subjects for signs and symptoms of pneumonitis
 
Evaluate subjects with suspected pneumonitis with radiographic imaging and initiate corticosteroid treatment
 
Add prophylactic antibiotics for opportunistic infections
 

	Grade 3 or 4, or recurrent Grade 2	Permanently discontinue		
Diarrhoea / Colitis	Grade 2 or 3	Withhold	
 
Administer corticosteroids (initial dose of 1-2mg/kg prednisone or equivalent) followed by taper
 
	
 
Monitor subjects for signs and symptoms of enterocolitis (i.e. diarrhea, abdominal pain, blood or mucus in stool with or without fever) and of bowel perforation (i.e. peritoneal signs and ileus).
 
Subjects with <math>\geq</math> Grade 2 diarrhea suspecting colitis should consider GI consultation and performing endoscopy to rule out colitis.
 
Subjects with diarrhea/colitis should be advised to drink liberal quantities of clear fluids. If sufficient oral fluid intake is not feasible, fluid and electrolytes should be substituted via IV infusion.
 

	Grade 4 or recurrent Grade 3	Permanently discontinue		
AST / ALT elevation or Increased Bilirubin	Grade 2	Withhold	
 
Administer corticosteroids (initial dose of 0.5- 1mg/kg prednisone or equivalent) followed by taper
 
	
 
Monitor with liver function tests (consider weekly or more frequently until liver enzyme value returned to baseline or is stable)
 

	Grade 3 or 4	Permanently discontinue		

Immune-related AEs	Toxicity grade or conditions (CTCAEv4.0)	Action taken to pembrolizumab	AE management with corticosteroid  and/or other therapies	Monitoring and Supportive Care

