Type 1 diabetes mellitus (T1DM) or Hyperglycemia	Newly onset T1DM or Grade 3 or 4 hyperglycemia associated with evidence of $\beta$ -cell failure	Withhold	
 
Initiate insulin replacement therapy for subjects with T1DM
 
Administer anti-hyperglycemic in subjects with hyperglycemia
 
	
 
Monitor subjects for hyperglycemia or other signs and symptoms of diabetes.
 

Hypophysitis	Grade 2	Withhold	
 
Administer corticosteroids to treat secondary adrenal insufficiency and initiate hormonal replacements as clinically indicated.
 
	
 
Monitor for signs and symptoms of hypophysitis (including hypopituitarism and adrenal insufficiency)
 

	Grade 3 or 4	Withhold until improved to Grade <2 and if controlled with hormone replacement. Otherwise permanently discontinue		
Hyperthyroidism	Grade 2	Continue	
 
Treat with non-selective beta-blockers (e.g. propranolol) or thionamides as appropriate
 
	
 
Monitor for signs and symptoms of thyroid disorders.
 

	Grade 3 or 4	Withhold until recovery to Grade $\leq$ 1. Otherwise permanently discontinue		
Hypothyroidism	Grade 2-4	Continue	
 
Initiate thyroid replacement hormones (e.g. levothyroxine or liothyroinine) per standard of care
 
	
 
Monitor for signs and symptoms of thyroid disorders.
 

Nephritis and renal dysfunction	Grade 2	Withhold	
 
Administer corticosteroids (prednisone 1-2mg/kg or equivalent) followed by taper.
 
	
 
Monitor for changes of renal function
 

	Grade 3 or 4	Permanently discontinue		
Skin Reactions	Grade 3	Withhold	
 
Based on severity of AE administer corticosteroids
 
	
 
Monitor for suspected severe skin reactions.
 

	Grade 4	Permanently discontinue		
Stevens-Johnson syndrome (SJS)	Suspected SJS or TEN	Withhold	
 
Refer to a specialist unit for assessment and treatment.
 
	
 
Monitor for suspected severe skin reactions.
 

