Immune-related AEs	Toxicity grade or conditions (CTCAEv4.0)	Action taken to pembrolizumab	AE management with corticosteroid  and/or other therapies	Monitoring and Supportive Care
or toxic epidermal necrolysis (TEN) suspected	Confirmed SJS or TEN	Permanently discontinue		
Myocarditis	Grade 1 or 2	Withhold	
 
Based on severity of AE administer corticosteroids
 
	
 
Ensure adequate evaluation to confirm etiology and/or exclude other causes
 

	Grade 3 or 4	Permanently discontinue		
All Other immune-related AEs	Intolerable/persistent Grade 2	Withhold	
 
Based on severity of AE administer corticosteroids
 
	
 
Ensure adequate evaluation to confirm etiology or exclude other causes
 

	Grade 3	Withhold or discontinue based on the type of event 		
	Grade 4 or recurrent Grade 3	Permanently discontinue		

*Footnotes: General Instructions for management of irAE*

1. Corticosteroid taper should be initiated upon AE improving to Grade 1 or less and continue to taper over at least 4 weeks.
2. For situations where pembrolizumab has been withheld, pembrolizumab can be resumed after AE has been reduced to Grade 1 or 0 and corticosteroid has been tapered. For subjects with Grade 3 or 4 immune-related endocrinopathy, pembrolizumab may be resumed when AE improves to Grade 2 or lower and is controlled with hormonal replacement therapy.
3. For situation where pembrolizumab is withheld initially, pembrolizumab should be **permanently discontinued** if AE does not resolve within 12 weeks of last dose or corticosteroids cannot be reduced to ≤ 10 mg prednisone or equivalent per day within 12 weeks.
4. For severe and life-threatening irAEs, IV corticosteroid should be initiated first followed by oral steroid. Other immunosuppressive treatment should be initiated if irAEs cannot be controlled by corticosteroids.
5. Events that require discontinuation include and not limited to: Gullain-Barre Syndrome, encephalitis

**Note:** For participants with Grade 3 or 4 immune-related endocrinopathy where withhold of pembrolizumab is required, pembrolizumab may be resumed when AE resolves to ≤ Grade 2 and is controlled with hormonal replacement therapy or achieved metabolic control (in case of T1DM).

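### Appendix 7 leaves open a permanent stop at 12 weeks that Table 4 footnote 3 directs, and it omits several of Table 4's other stops

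*Protocol*

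**What the plan says.** **Table 4 (Protocol Section 7.5).** Footnote 3 covers a drug that was initially withheld. It directs permanent discontinuation "if AE does not resolve within 12 weeks of last dose or corticosteroids cannot be reduced to" 10 mg prednisone or equivalent a day or less within 12 weeks. The footnotes are headed as general instructions for irAEs, although the marker for footnote 3 appears only in the pneumonitis row. Table 4 also lists organ-specific permanent stops:

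- pneumonitis at "Grade 3 or 4, or recurrent Grade 2";
- AST/ALT or bilirubin elevation, "Nephritis and renal dysfunction", and myocarditis, each at Grade 3 or 4;
- "Confirmed SJS or TEN";
- event types named in footnote 5, such as encephalitis.

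**Appendix 7 (Events of Clinical Interest).** For an irAE still above Grade 1 at 12 weeks after the last dose, "study therapy discontinuation should be considered after discussion with PePS2 Trial Office". On restart: "Pembrolizumab may be restarted within 12 weeks after last dose if the adverse reaction remains at Grade" 1 or less with prednisone at 10 mg a day or less. On mandatory stops: "Pembrolizumab must be permanently discontinued for any Grade 3 immune-related adverse reaction that recurs", and likewise for Grade 4 reactions, except endocrinopathies controlled with replacement hormones. It also says: "Permanent discontinuation of pembrolizumab due to irAE may be subject of discussion between the Trial Office and treating Investigator".

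**Cross-references.** Section 7.11 sends the reader to Section 7.5 for discontinuation details, and Section 7.5 sends the reader to Table 4. Section 9.1.3, within the reporting section, refers to Appendix 7 for immune-mediated events. No sentence states that one text overrides the other.

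**The concern.** A stopping rule for toxicity should give every site the same answer for the same patient. At 12 weeks it does not: one text tells the site to stop for good, and the other asks it to consider stopping after a conversation. Both are operative text in the current protocol.

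What is at stake is patient safety and uniform conduct. The population is frail (ECOG performance status 2). The patients concerned are those whose irAE has been slow to resolve or who still depend on steroids, and for them continued or renewed exposure is a serious decision.

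**Working it through.** No arithmetic applies, so the check sets the two texts side by side.

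| Situation | Table 4 | Appendix 7 | Relation |
|---|---|---|---|
| Drug withheld; irAE above Grade 1 at 12 weeks after last dose | Permanent stop (footnote 3) | Consider stopping, after discussion | Direct conflict |
| irAE at Grade 1 or less, but steroid still above 10 mg a day at 12 weeks | Permanent stop (footnote 3) | 12-week sentence silent; restart condition not met | Omission |
| First Grade 3 pneumonitis, hepatic event, nephritis or myocarditis | Permanent stop | Not on the must-stop list | Omission |
| Recurrent Grade 2 pneumonitis | Permanent stop | Not on the list | Omission |
| Confirmed SJS/TEN, unless Grade 4 or recurrent Grade 3 | Permanent stop | Not on the list | Omission |
| First Grade 3 event of a footnote 5 type | Permanent stop | Not on the list | Omission |
| Diarrhoea/colitis, or other irAE: Grade 4 or recurrent Grade 3 | Permanent stop | Permanent stop | Agree (hormone-controlled endocrinopathies aside) |
| Recurrent Grade 3 skin reaction | Skin row silent on recurrence | Permanent stop | Appendix 7 stricter |

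**Step 1: is the 12-week difference real?** Both sentences use the same clock, 12 weeks from the last dose. An irAE above Grade 1 at that point has neither resolved nor improved to Grade 1, so it meets both conditions. Footnote 3 then settles the outcome, and Appendix 7 leaves it open. A site that follows Appendix 7 faithfully could decide not to stop, which footnote 3 does not allow.

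**Step 2: how far does the looseness go?** Appendix 7's restart sentence closes its own window at 12 weeks. So Appendix 7 fails to require the stop, but no sentence in it authorises a restart after 12 weeks. The steroid limit appears in the restart sentence but is missing from the 12-week stop.

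**Step 3: does it reach the primary analysis?** The toxicity co-primary outcome counts a treatment-related dose delay or a discontinuation due to an adverse event. Dosing is every 3 weeks. A patient withheld for a treatment-related event until 12 weeks after the last dose has already missed the dose due at week 3 and is already an event. Choosing between stopping and not stopping at week 12 does not change that classification. For the omitted organ-specific stops, withholding that delays a dose and permanent discontinuation also both count. The decision rule and the sample size of 60 do not depend on which text is followed.

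**Step 4: would a bare statement that Table 4 prevails be enough?** No. Footnote 2 and the Note under Table 4 let a patient with a Grade 3 or 4 endocrinopathy resume at Grade 2 or lower on hormone replacement, or with metabolic control in type 1 diabetes. Such an event may never resolve. Read literally, footnote 3 would stop for good a patient whom footnote 2 allows to resume.

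**The case against.** The strongest reply is that the protocol already assigns discontinuation to one place. Section 7.11 points to Section 7.5, and Section 7.5 points to Table 4. Appendix 7 calls itself general guidance and warns that it may be incomplete. The Section 9.1.3 pointer to it concerns which events are reported. Its 12-week sentence also requires discussion with the Trial Office, so a site could not act on it alone. All of this stands and is why the practical risk is low. It does not remove the conflict: a cross-reference is not a precedence rule, and Appendix 7 gives its own dosing instructions without deferring to Table 4.

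Four stronger readings are tempting, and the documents support none of them.

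- *Appendix 7 permits re-dosing after a first Grade 3 pneumonitis or myocarditis.* Its list says when the drug must stop, and does not say that it must stop only then. The restart sentence follows a paragraph on withholding, so it can be read as restart after withholding, in line with footnote 2. A site can obey both texts by following Table 4.
- *Appendix 7 allows restart after 12 weeks.* It does not, as step 2 shows.
- *The sentence about discussing permanent discontinuation overrides Table 4.* It comes straight after one about cases that the current guidelines do not cover, so it need not loosen any Table 4 stop.
- *The number of affected patients can be estimated from the background rates.* Section 1.1.2 gives Grade 3 or higher pneumonitis as 1.8% and transaminitis as 0.6%. Section 1.2.1 says the trials reported so far enrolled performance status 0-1. These rates include Grade 4, where both texts stop, and they say nothing about non-resolution at 12 weeks or about re-dosing. They neither measure nor bound the problem.

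**Conclusion.** The protocol is wrong as written on the 12-week stop: footnote 3 directs permanent discontinuation, Appendix 7 asks only that it be considered, and Appendix 7 leaves the steroid trigger out of that stop. The missing organ-specific stops are a secondary weakness, by omission only.

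Severity is minor. The effect is on patient safety and consistency between sites. There is no effect on the toxicity co-primary outcome, the decision rule or the sample size, and no patient count should be attached. This rests on two readings: that footnote 3 applies to irAEs generally, as the heading over the footnotes indicates, and that sites treat Table 4 as controlling, as Sections 7.5 and 7.11 suggest.

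**What to change.** 1. Replace the restart, permanent-stop and 12-week sentences in Appendix 7 with: *Withholding, restart and permanent discontinuation follow Section 7.5 and Table 4, which prevail.*
2. Add to Table 4 footnote 3: *except endocrinopathies controlled with hormone replacement or with metabolic control, as in footnote 2 and the Note.* Without this, the first change leaves footnote 3 at odds with footnote 2.
3. Before deleting Appendix 7's stop for recurrent Grade 3 reactions, decide whether to carry it into Table 4's skin row, which is silent on recurrence. This is a clinical decision for the sponsor.
4. Optionally, confirm that withholding for Grade 4 hyperthyroidism in Table 4 is intended, since Appendix 7 exempts only endocrinopathies controlled with replacement hormones.

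The cost is a wording amendment and one notice to sites. The amendment may have to be a substantial one, since Amendment 7, which updated Table 4, was logged as substantial. No patients, procedures or analyses are added.
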